4.5.3 Investigational Product Preparation

MEDI-565 is supplied as a lyophilized Drug Product requiring reconstitution prior to use. The reconstitution should be performed with 0.7 mL sterile water for injection (WFI) for each vial with the liquid added gently to the side of the vial to minimize product foaming. The vial should be gently rotated or swirled for 30 seconds or until dissolution is complete. Do not shake or vigorously agitate the vial. Reconstituted MEDI-565 should stand undisturbed at room temperature for a minimum of 5 minutes or until the solution clarifies. The reconstituted solution should appear clear or slightly opalescent. A thin layer of bubbles on the liquid surface is considered normal. MEDI-565 IV Bag Protectant is supplied as a ready-to-use liquid that should appear as a clear to slightly opalescent, colorless to slightly yellow liquid. Allow the vials selected for administration to come to room temperature. The volumes of reconstituted MEDI-565 Drug Product and MEDI-565 IV Bag Protectant to be added to the IV bag are calculated as described below.

Calculations:

The volume of MEDI-565 IV Bag Protectant to be added to the IV bag is equal to 5% of the nominal volume of the IV bag:

$$\text{Volume of IV Bag Protectant (mL)} = \text{IV bag nominal volume} \times 0.05$$

For example, in preparing a 100 mL IV bag the following amount of MEDI-565 IV Bag Protectant will be required:

$$100 \text{ mL IV bag} \times 0.05 = 5.0 \text{ mL MEDI-565 IV Bag Protectant}$$

The volume of reconstituted MEDI-565 Drug Product (dose volume) for IV infusion is calculated based on the dose using the following formula:

$$\text{Dose Volume (mL)} = \text{Dose Level (mg/day)} \div \text{Concentration (0.5 mg/mL)}.$$

For example, a subject scheduled to receive a dose of MEDI-565 at 0.6 mg/day will require the following amount:

$$0.6 \text{ mg/day} \div 0.5 \text{ mg/mL} = 1.2 \text{ mL dose volume}.$$

The dose of investigational product for administration must be prepared by the investigator's or site's designated investigational product manager using aseptic technique. The volume of

0.9% sodium chloride solution equivalent to the calculated MEDI-565 dose volume plus the volume of IV Bag Protectant must first be removed. This step is then followed, in order, by the addition of the calculated volume of the IV Bag Protectant and then the MEDI-565 dose volume. The bag should be gently and thoroughly mixed after addition of the IV Bag Protectant and again after addition of MEDI-565.

MEDI-565 and IV Bag Protectant do not contain preservatives and any unused portion must be discarded. Total in-use storage time from reconstitution of MEDI-565 to start of administration should not exceed 4 hours at room temperature or 24 hours at 2°C to 8°C. If in-use storage time exceeds these limits, a new dose must be prepared from new vials.

The entire volume of the 100 mL IV bag should be administered over 3 hours and followed by a 20 mL flush of normal saline. The end of the infusion is the time after the flush has been administered.

The MEDI-565 Dose Preparation Table will be utilized to ensure correct dose preparation. For doses less than or equal to 120 µg/day, MEDI-565 must be prepared in two dilution steps. For doses greater than 120 µg/day, MEDI-565 must be prepared in one dilution step (see [Appendix 5](#)).

4.5.4 Investigational Product Administration

The day of receipt of the first dose of investigational product is considered Day 1. For each treatment cycle, MEDI-565 will be administered by IV infusion over 3 hours per day for 5 consecutive days.

Under Amendment 4 of the protocol and as part of the overall risk mitigation plan for infusion-associated hypoxia, prophylactic dexamethasone (8 mg) or equivalent will be administered at the following 4 time points during Cycle 1, Day 1:

- 8 hours (± 15 minutes) and within 30 minutes PRIOR to the start of MEDI-565 infusion, and
- 8 hours (± 15 minutes) and 16 hours (± 15 minutes) AFTER the start of MEDI-565 infusion.

This regimen or equivalent may be followed during subsequent MEDI-565 infusions per the investigator's clinical judgment.

4.5.4.1 Monitoring of Dose Administration

Subjects will be monitored with assessment of vital signs and pulse oximetry at the following time points: within 15 minutes prior to the start of infusion, every 0.5 hours (\pm 5 minutes) during infusion, immediately post end of infusion (EOI) (\pm 5 minutes), and 0.5 hours (\pm 5 minutes), 1 hour (\pm 5 minutes), and 2 hours (\pm 15 minutes) after the EOI.

Specifically on Cycle 1, Day 1, monitoring of vital signs and pulse oximetry will continue beyond the 2 hour post EOI time point until the start of infusion on Cycle 1, Day 2 as follows:

- 4 hours (\pm 15 minutes), 6 hours (\pm 15 minutes), and 8 hours (\pm 15 minutes) post EOI
- 12 hours (\pm 15 minutes), 16 hours (\pm 15 minutes), 20 hours (\pm 15 minutes), and 24 hours (\pm 15 minutes) post EOI

As with any antibody, allergic reactions to dose administration are possible. Therefore, appropriate drugs and medical equipment to treat acute anaphylactic reactions must be immediately available, and study personnel must be trained to recognize and treat anaphylaxis.

With MEDI-565, the most frequent acute signs/symptoms observed with study drug infusions and assessed as drug-related included: fever, shaking chills, nausea, vomiting, abdominal pain, headache and hypoxia. In the event that such adverse events are noted and are clinically significant, in the absence of a clear alternative etiology, consider steroid treatment (8 mg dexamethasone every 8 hours, or equivalent) until evidence of resolution. If a subject experiences any symptoms such as those listed above, further dosing should be delayed until the subject is clinically stable and the symptoms are resolved. If steroids are clinically indicated to manage any Grade 3 or higher infusion-related signs/symptoms, all remaining doses in the current cycle should be aborted. If steroids are clinically indicated to manage any Grade 2 or lower infusion-related signs/symptoms, the infusion rate should be decreased for the current dose and all remaining doses in the cycle.

In the event of an infusion-related reaction, the infusion of MEDI-565 may be decreased by 50% or interrupted until resolution of the event (up to 4 hours) and reinitiated at 50% of the initial rate until completion of the infusion. Acetaminophen and/or an antihistamine (eg. diphenhydramine) may be administered at the discretion of the investigator as long as liver function tests (LFTs) are within normal limits. If the infusion reaction is severe or prolonged, glucocorticoids (dexamethasone 8 mg every 8 hours, or equivalent, or by standard

institutional practice) should be administered as well following best medical practice. For subsequent infusions in subjects who experience an infusion reaction and do not require discontinuation of MEDI-565 (see [Table 4.5.4.4-1](#)), acetaminophen and an antihistamine may be administered prior to initiation of the MEDI-565 infusion.

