4.2.3 Withdrawal Criteria

An individual subject will not receive any further investigational product if any of the following occur in the subject in question:

- 1) Withdrawal of consent or lost to follow-up
- 2) Any AE, that, in the opinion of the investigator or the sponsor, contraindicates further dosing
- 3) Subject is determined to have met one or more of the exclusion criteria for study participation (such subjects will be replaced if identified during the DLT period in the dose-escalation phase or at any point in the expansion phase)
- 4) Pregnancy or intent to become pregnant (see Section 6.4.3.3)
- 5) Documentation of PD
If radiographic changes are believed by the investigator to be secondary to drug induced inflammation and not tumor progression, the investigator may postpone a diagnosis of PD until the next scheduled radiographic evaluation in the study (Wolchok et al, 2009).
- 6) Subject noncompliance
- 7) Initiation of alternative anti-cancer treatment
- 8) Treatment with another investigational agent
- 9) Dose-limiting toxicity (see Section 4.5.4.5 for definition of DLTs)
- 10) After Cycle 1 (protocol-defined DLT period), any events of unacceptable toxicity (as defined by DLT criteria). Exceptions to this may be granted on a case-by-case basis

for subjects who are receiving clinical benefit and whose unacceptable toxicity resolves within 7 days, and must be agreed to in conjunction with the FDA (see Section 4.5.4.4)

- 11) After Cycle 1 (protocol-defined DLT period), any events where MEDI-565 treatment is interrupted and a cycle is delayed more than 7 days for reasons of toxicity, or treatment is delayed more than once during the study (see Section 4.5.4.4)
- 12) Occurrence of an acute infusion reaction or cytokine release syndrome resulting in pyrexia, chills, or NCI CTCAE v4.03 Grade 2 hypotension that does not allow for the completion of the infusion within 6 hours from the start of the infusion despite a slowing of the infusion rate or treatment with fluids, antihistamines, or steroids
- 13) Occurrence of a Grade 3 or greater event as a component of the cytokine release syndrome
- 14) Occurrence of a suspected immunoglobulin E (IgE)-mediated allergic reaction (ie. presence of urticaria or bronchospasm)
- 15) Significant medical events that in the opinion of the medical monitor or investigator warrant subject discontinuation.

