4.5.4.4 Dose Modification for Toxicity Management

Management of Dose Interruption During Infusion

The MEDI-565 infusion will be stopped immediately for the following events:

- The subject experiences a DLT as defined in Section 4.5.4.5
- The subject meets criteria for temporary or permanent discontinuation of MEDI-565 as described in Section 4.2.3
- The investigational product is incorrectly prepared or administered (eg, overdose)
- There is a technical problem with the infusion pump

The MEDI-565 infusion may be restarted according to the criteria listed below:

- If the MEDI-565 infusion is interrupted for reasons other than toxicity, it can be restarted at the same dose with no additional measures required
- If the MEDI-565 infusion is interrupted for management of toxicity, it may be restarted according to the guidelines in Table 4.5.4.4-1

Dose Modification Following the DLT Period

Following the DLT period, any unacceptable toxicity (as defined by the DLT criteria) will result in the discontinuation of MEDI-565; subjects who have DLT-like events after the DLT period will not be retreated with MEDI-565. Exceptions to this may occur on a case-by-case basis for subjects who have experienced clinical benefit and whose unacceptable toxicity resolves within 7 days. Decisions to retreat such subjects will be made in conjunction with the FDA.

For other toxicities observed following completion of the DLT period, subsequent cycles of MEDI-565 may be delayed or modified as described in [Table 4.5.4.4-1](#). Both hematologic and nonhematologic toxicities will be graded according to [NCI CTCAE v4.03](#).

Table 4.5.4.4-1 MEDI-565 Dose Modification Table (Cycle 2 and Greater)

Hematologic or Nonhematologic Toxicity	Dose Modification of MEDI-565
≤ Grade 1	None
Grade 2	
For AEs occurring during treatment with MEDI-565, do not stop infusion. The infusion may be slowed but must be completed within 6 hours. Grade 2 hypotension, pyrexia or chills that do not respond to medical therapy and do not allow completion of the infusion within 6 hours will result in permanent discontinuation of MEDI-565.
 
For AEs present at the end of the treatment cycle, delay next cycle of MEDI-565 for up to 7 days until resolution to ≤ Grade 1 or baseline, and resume at current dose level.
 
If AE does not resolve to ≤ Grade 1 or baseline within 7 days of the end of the cycle, initiate next cycle at 50% of current dose level.

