Table 4.5.4.4-1 MEDI-565 Dose Modification Table (Cycle 2 and Greater)

Hematologic or Nonhematologic Toxicity	Dose Modification of MEDI-565
Grade 3 or 4	
First Occurrence^a :
 
Discontinue MEDI-565 if toxicity meets the criteria for DLT as defined for the first cycle of treatment (see Section, 4.5.4.5) including Grade 3 or 4 cytokine release syndrome or allergic reactions. Subjects who experience a Grade 3 or 4 toxicity that meets DLT criteria that resolves within 7 days (except cytokine release syndrome or allergic reaction) and who are demonstrating clinical benefit may be allowed to continue receiving MEDI-565 following consultation with FDA.
 
For Grade 3 or 4 toxicities that do not meet DLT criteria and resolve to Grade 1 or baseline within 7 days MEDI-565 may be continued at 50% of current dose level.
 
For acute infusion reactions, AEs will be treated symptomatically and the rate of infusion may be slowed. If infusion is completed within 6 hours, subsequent doses of MEDI-565 may resume at 50% of current dose level. If infusion is not completed within 6 hours, discontinue MEDI-565.
 
Second Occurrence^a :
 
Discontinue MEDI-565.

^a Refers to the first or second occurrence of a Grade 3 or 4 toxicity in a given subject, at any dose level, for any cycle after Cycle 1

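### A permitted 4-hour interruption with half-rate restart cannot fit the 6-hour completion limit where that limit applies, and it is unsettled how a Cycle 1 subject stopped for a non-DLT infusion reaction is counted

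*Protocol*

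**What the plan says.** **Planned infusion.** Section 4.5.4 states that "MEDI-565 will be administered by IV infusion over 3 hours per day for 5 consecutive days". Section 4.5.3 adds a 20 mL flush and states that "The end of the infusion is the time after the flush has been administered".

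**Interruption.** Section 4.5.4.1 lets the infusion rate be halved, or the infusion be "interrupted until resolution of the event (up to 4 hours) and reinitiated at 50% of the initial rate until completion of the infusion".

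**Completion limit.** Section 4.2.3 item 12 ends treatment when a reaction with pyrexia, chills or Grade 2 hypotension prevents "completion of the infusion within 6 hours from the start of the infusion despite a slowing of the infusion rate". It names no cycle. Table 4.5.4.4-1 is headed Cycle 2 and Greater. For Grade 2 events it tells sites to keep the infusion running and adds: "The infusion may be slowed but must be completed within 6 hours". For Grade 3 or 4 acute infusion reactions it says "If infusion is completed within 6 hours, subsequent doses of MEDI-565 may resume at 50% of current dose level", and otherwise treatment is discontinued. The text of Section 4.5.4.4 refers restarts after any toxicity interruption to this table, without a cycle restriction.

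**Grade 3 reactions.** Section 4.5.4.1 says "If steroids are clinically indicated to manage any Grade 3 or higher infusion-related signs/symptoms, all remaining doses in the current cycle should be aborted". Its next paragraph calls for glucocorticoids when a reaction is severe or prolonged and does not mention aborting doses. Section 4.2.3 item 13 ends treatment if a Grade 3 or greater event is part of cytokine release syndrome.

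**DLT counting.** Exception 5 in Section 4.5.4.5 takes a Grade 3 infusion-related event that resolves within 12 hours without sequelae out of the DLT definition. Section 4.5.4.2 rule 1 requires either all of Days 1-5 of Cycle 1 plus follow-up, or a DLT, for evaluability. Sections 4.2.4 and 4.5.4.5 replace subjects who stop, or lack a full cycle, for reasons other than a DLT. The Sample Size part of the Study Abstract limits nonevaluable subjects to those discontinued for reasons other than toxicity related to study drug.

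**The concern.** A site that uses the interruption in Section 4.5.4.1 to its limit can, for the symptoms and cycles covered, bring the subject under a rule that ends treatment. For Grade 2 events from Cycle 2 onward, one section permits a stop that the table forbids. For a Grade 3 reaction, the next dose may be omitted, given at half the dose level, or permanently withheld, depending on which rule is read first.

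The statistical stake is the Cycle 1 count behind the MTD. Amendment 4 takes escalation back through 3 mg, where two of five subjects had dose-limiting hypoxia within hours of the first infusion. Section 3.4 names cytokine release as a possible contributor. With 3 to 6 evaluable subjects per cohort, the classification of a single subject can change an escalation decision.

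**Working it through.** **1. The plan's own figure.** Table 7.5-1 gives the probability of escalating under the 3+3 rule. With true DLT rate p it is (1-p)^3 + 3p(1-p)^2 x (1-p)^3. For p = 10% to 90% this gives 0.906, 0.709, 0.494, 0.309, 0.172, 0.082, 0.032, 0.0088 and 0.001. All nine agree with the table, so the table is not in dispute.

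**2. Infusion time.** Inputs are the 3-hour infusion (4.5.4), the interruption of up to 4 hours with restart at 50% (4.5.4.1), and the 6-hour limit (4.2.3 item 12; Table 4.5.4.4-1). Let t be the hours run at full rate (0 to under 3) and d the hours interrupted. The remaining 3 - t hours of infusion take (3 - t)/0.5 hours at half rate, so

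T = t + d + 2(3 - t) = 6 - t + d,

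and T is at most 6 only if d is at most t.

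| d (h) | t = 0.5 | t = 1 | t = 2 | t = 2.5 |
|---|---|---|---|---|
| 0 (slowing only) | 5.5 | 5.0 | 4.0 | 3.5 |
| 1 | 6.5 | 6.0 | 5.0 | 4.5 |
| 2 | 7.5 | 7.0 | 6.0 | 5.5 |
| 3 | 8.5 | 8.0 | 7.0 | 6.5 |
| 4 | 9.5 | 9.0 | 8.0 | 7.5 |

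For d = 4, T = 10 - t: 10 hours if the reaction comes at the very start, falling towards 7 as t approaches 3. Since t is below 3, every interruption of 3 hours or more breaches the limit. The flush belongs to the infusion but has no stated duration, so these totals are lower bounds.

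**3. One Cycle 1 event under different sections.** Take a Grade 3 infusion-related event, treated with steroids, that resolves within 12 hours without sequelae. By exception 5 it is not a DLT.

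- If the steroid sentence in 4.5.4.1 or item 13 of 4.2.3 is applied, doses stop. There is neither a full cycle nor a DLT, so the subject is not evaluable under 4.5.4.2.
- If only the following paragraph of 4.5.4.1 is applied, the subject can complete Days 1-5 and be an evaluable non-DLT.
- Once doses have stopped, 4.5.4.5 (no full cycle) and 4.2.4 (discontinued) replace the subject. The Study Abstract does not class a subject discontinued for study drug-related toxicity as nonevaluable, so there the subject is not replaced.

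**4. Illustrative size.** The documents give no frequency for such events. Assume that a fraction a = 5% to 20% of enrolled subjects have one, and compare keeping all of them with replacing all of them. If they are kept as non-DLTs, the rate among evaluable subjects stays p. If they are replaced, it becomes p/(1-a), and 3/(1-a) subjects must be enrolled per 3 evaluable.

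| p | Kept | Replaced, a = 5% | a = 10% | a = 20% |
|---|---|---|---|---|
| 10% | 0.906 | 0.897 | 0.887 | 0.862 |
| 20% | 0.709 | 0.686 | 0.660 | 0.600 |
| 30% | 0.494 | 0.462 | 0.428 | 0.351 |

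For example, with p = 20% and a = 20%, p/(1-a) = 0.25 and the escalation probability is 0.75^3 + 3(0.25)(0.75^5) = 0.600. Enrolment per 3 evaluable subjects rises to 3.16, 3.33 and 3.75.

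**The case against.** The best defence is that each rule has its own scope. Item 12 names only pyrexia, chills and Grade 2 hypotension, and the other 6-hour limits sit in a table headed Cycle 2 and Greater. On those terms, a Cycle 1 interruption for hypoxia, vomiting, abdominal pain or headache has no 6-hour limit. Four hours is a ceiling within a permission. Halving the rate without stopping takes 6 - t hours and complies before the flush, as does any interruption no longer than the time already infused. The Grade 3 rules have partly different triggers: steroids indicated, a component of cytokine release syndrome, or completion within 6 hours. The table agrees with item 13 on Grade 3 or 4 cytokine release syndrome.

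All of this stands, and it limits the point. A reader might infer that every interruption breaches a universal limit, or that following 4.5.4.1 necessarily forces withdrawal. The documents support neither. Nor is exception 5 a further conflicting treatment instruction: it classifies events for DLT counting, and a non-DLT event may end treatment without contradiction. The table's half-dose rule and its Grade 2 rule cannot be said to alter the Cycle 1 count while the table is confined to Cycle 2 onward.

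The defence does not remove the conflict for the symptoms and cycles the limit does cover, or the Grade 2 conflict from Cycle 2 onward. Because 4.5.4.4 refers toxicity restarts to the table without a cycle restriction, the table's Cycle 1 scope is itself unclear. Different triggers do not settle an event that meets several of them, and no precedence is given.

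**Conclusion.** The point holds in this limited form. Where the 6-hour limit applies, an interruption longer than the time already infused breaches it, and a full 4-hour interruption overshoots by more than 1 and up to 4 hours before the flush. This is arithmetic on the protocol's own figures and needs no outside assumption.

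The Cycle 1 evaluability problem also holds. It rests on Sections 4.2.3 item 13, 4.5.4.1, 4.5.4.2 and 4.5.4.5, and on the conflict between the Study Abstract and Section 4.2.4 over who is nonevaluable. A reader might infer that the MTD count is known to be distorted. The documents do not support that, because they give no frequency for these reactions and the escalation probabilities above depend on the assumed 5% to 20%. No sample-size, significance-level or power input is in question. The correction is worthwhile because it is cheap and bears on both safety handling and the primary endpoint.

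**What to change.** Reconcile Section 4.2.3 items 12-13, Section 4.5.4.1 and Section 4.5.4.4 with its table, so that interruption length, restart rate and completion limit are arithmetically compatible, with the flush explicitly included in or excluded from the limit. Remove the conflict over stopping for Grade 2 events. State which cycles Table 4.5.4.4-1 governs, and which rule takes precedence when one Grade 3 reaction meets several. The clinical values and the choice between rules are for the clinical team.

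Use one definition of a nonevaluable subject in the Study Abstract and Sections 3.1, 4.2.4, 4.5.4.2, 4.5.4.5 and 7.2. It should say how a Cycle 1 subject stopped for a non-DLT infusion reaction is counted and whether that subject is replaced.

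The cost is amendment wording and a memo to sites. No new data are needed.

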4.5.4.2 Dose Escalation

Rules for dose escalation are as follows:

- 1) The MTD will be determined based on the assessment of a DLT (refer to Section [4.5.4.5](#)) during the DLT period, which is defined as the time from the first dose of MEDI-565 to 28 days after the first dose of MEDI-565 (Cycle 1). Subjects are considered evaluable for assessment of DLT if they receive at least 1 full cycle of MEDI-565 (Days 1-5, Cycle 1) and complete the safety follow-up (Days 6-28, Cycle 1) through the DLT evaluation period or experience any DLT. Nonevaluable subjects will be replaced.
- 2) If a Grade 3 or greater AE or toxicity corresponding to a DLT occurs in any cohort, that cohort will be expanded to 6 evaluable subjects. If 1 of 6 subjects experiences a DLT in the expanded cohort, dose escalation will proceed to the next dose level. If ≥ 2 subjects experience a DLT in a given cohort, the MTD will have been exceeded and the next lower dose will be evaluated as the MTD. The MTD will be defined as the highest dose, up to 10 mg, at which no more than 1 out of 6 subjects experience a DLT.
- 3) If the MTD is exceeded during dose escalation (≥ 2 out of 6 subjects experience a DLT in a given cohort), and the prior lower dose level is demonstrated to be safe (≤ 1 out of 6 subjects with DLTs), an intermediate dose may be evaluated if appropriate based on available PK, pharmacodynamics, safety, and clinical data. Dose escalation must stop prior to reaching the dose and exposure for the cohort that exceeded the MTD.
- 4) If significant antitumor activity is observed during dose escalation prior to identifying an MTD and before reaching the 10 mg dose, the Sponsor may halt dose escalation without determining the MTD. In this case, an OBD below the MTD may be chosen for the dose-expansion phase of the study, provided this is supported by the safety, antitumor activity, PK, pharmacodynamic, and biomarker data.

A study-specific Dose Escalation Committee will provide ongoing safety surveillance of the study, with regularly scheduled reviews of safety and other relevant data. This committee will be responsible for dose-escalation decisions and making recommendations regarding further conduct of the study. The sponsor will notify sites when enrollment into each dose cohort has been completed and when enrollment into the next dose cohort is permitted. In addition, MedImmune's internal safety monitoring committee (ie, SMC or equivalent), provides safety

surveillance, guidance, and oversight for all clinical development trials in which MedImmune has sponsor accountabilities. Details of the composition and role of the Dose Escalation Committee and the SMC (or equivalent) are presented in Section 6.5.

At the discretion of the sponsor, an intermediate dose may be chosen for dose escalation. Situations that might prompt selection of an intermediate dose include unexpected toxicities that do not meet the definition of DLT or multiple similar toxicities in a cohort that do not meet definition of a DLT. If an intermediate dose is chosen, dose escalation will be to the next listed dose, provided all the criteria for dose escalation above are met. Further escalation will be based on toxicities observed at each dose level, and may proceed on the original schedule or include additional intermediate steps based on accumulated safety data.

